11.1.5 Duration of Response

Duration of overall response: The duration of overall response is measured from the time measurement criteria are met for CR or PR (whichever is first recorded) until the first date that recurrent or progressive disease is objectively documented (taking as reference for progressive disease the smallest measurements recorded since the treatment started).

The duration of overall CR is measured from the time measurement criteria are first met for CR until the first date that recurrent disease is objectively documented.

Duration of stable disease: Stable disease is measured from the start of the treatment until the criteria for progression are met, taking as reference the smallest measurements recorded since the treatment started.

11.1.6 Progression-Free Survival (PFS)

PFS is defined as the duration of time from start of treatment to time of progression or death, whichever occurs first.

11.1.7 Overall Survival (OS)

OS is defined as the duration of time from start of treatment to the time of death

11.1.8 Response Review

Review process

Independent response review involves:

1. Reviewing the disease status at 6 months (tumor evaluation at 6-months or earlier in case of disease progression) in comparison with baseline (primary objective).
2. Reviewing all responses (complete and partial) observed during the study period.

Independent response review will proceed as follows:

- The review process will be centralized at Institut Bergonié and will be performed by one independent radiologist expert in bone sarcomas.
- When reviewing the 6-month disease status, the reviewer will only be provided with the first 6-month patient information.
- Patient' files will be anonymous.

In case of discordance between the local radiologist and the reviewer, the judgment provided by the expert reviewer will be retained and used for response evaluation in statistical analyses.

Review process schedule

The Simon's two-stage ([section 13](#)) implies evaluating treatment efficacy after 17 patients at the first stage, and then once all 51 patients have been included.

Review will thus be implemented in two steps:

- Once 6-month information is available for the first 17 patients;
- At the end of the study.

Practical implementation

- Each site must send the completed “Baseline Clinical Subject Profile” ([Appendix JA](#)) with the first shipment.
- For each shipment, media should be accompanied by the completed “Radiology Referral Form” ([Appendix JB](#)).
- The reviewer will assess the response to therapy, document the results on the “Response Review Form” ([Appendix JC](#)) and sign this form.
- Patient’s information must be recorded on an imaging CD.
- Once 6-month response is available, each site must send the imaging CD to Institut Bergonié as soon as possible.
- Once complete patient’s follow-up has ended, an updated imaging CD must also be sent to Institut Bergonié
- All CDs must be sent to :

| |
|--|
| 
[name], Responsible Clinical research Assistant Institut Bergonié, [name], [name], France Phone: [name] – mail : [contact]
 |
|--|

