| STUDY POPULATION Translational research study | All patients included in the trial are eligible for the translational research study. |
| NUMBER OF PATIENTS | Based on the following hypotheses under GDC-0449 treatment: 20% clinical benefit (null hypothesis), 40% acceptable clinical benefit (alternative hypothesis), 10% type I error rate, 90% power, a total of 37 assessable patients will be necessary (17 for the first stage + 20 for the second stage). In order to account for not assessable patients (+/- 20%), 45 patients will be recruited. |
| NUMBER OF SITES | This is a multicenter study. A complete list of investigators will be provided as a separate document. |
| STUDY DRUG FORMULATION | GDC-0449 – Capsules packaged in 75 mL bottles. Each bottle contains 32 capsules. |
| ROUTE OF ADMINISTRATION | GDC-0449: Oral |
| ADMINISTERED DOSE | GDC-0449: 150 mg, take with or without food at the same time every day |
| TREATMENT SCHEDULE | GDC-0449: Days 1-28 |

| | |
|---------------------------------------|--|
| EFFICACY EVALUATIONS | 
Patients will be evaluated for efficacy if they receive at least one complete or two incomplete cycles of GDC-0449, and if they have at least one disease measurement recorded not less than eight weeks after treatment onset (except for in case of early disease progression).
 
Antitumor activity will be assessed using RECIST on a set of measurable lesions identified at baseline as target lesions and followed until disease progression by the appropriate method (computed tomography [CT] scan or magnetic resonance imaging [MRI]).
 
Radiological and clinical (whenever appropriate) tumor assessment will be performed at baseline and every eight weeks until evidence of disease progression (PD). Whenever the criteria of response are met, the appropriate imaging tests will be repeated at least four weeks later in order to confirm the response. Beyond 48 months of treatment without evidence of progressive disease, radiological tumor assessment will be performed every 3 months.
 
Efficacy will be evaluated based on 6-month clinical benefit rate (primary objective), best overall response, 1- and 2-year PFS, and 1- and 2-year OS.
 |

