13.2 Sample Size/Accrual Rate

The data from the literature about survival of patients with advanced chondrosarcomas are almost non-existent. However, some studies confirm that the prognosis of patients with metastatic chondrosarcomas is poor and similar to that observed in metastatic soft-tissue tumors with median survival ranging from 7 to 17 months ([Dickey et al., 2004](#); [Ries et al., 2007](#); [Giuffrida et al., 2009](#)). Therefore, we believe that a 6 months clinical benefit rate of 40% is a reasonable objective in this setting. This objective was also chosen by American investigators (SARC) in a phase 2 trial of perifosine in patients with chemo-insensitive sarcomas (including chondrosarcomas).

We rely on an optimal two-stage Simon's design (Simon, 1989). Based on the following hypotheses under GDC-0449 treatment:

- 20% non-progression rate (null hypothesis),
- 40% acceptable non-progression rate (alternative hypothesis),
- 10% type I error rate,
- 90% power,

a total of 37 assessable subjects will be necessary, with 17 assessable subjects recruited to the first stage.

Stage 1: Following the inclusion of the first 17 assessable patients, if 3 or less patients are progression-free (complete response, partial response or stable disease), the study would be terminated early. Otherwise, the second group of 20 subjects will be recruited.

Stage 2: If at the end of recruitment, 11 patients or more are progression-free (out of the 37 evaluable patients), GDC-0449 would be considered worthy of further testing in this disease.

To be evaluable, a subject must meet the eligibility criteria AND have received at least one complete or two incomplete cycles of GDC-0449 AND at least one disease measurement recorded not less than eight weeks after treatment onset.

Given the disease is rare and the absence of standard treatment in this indication, inclusion will not be suspended after the recruitment of the first 17 patients. Inclusion will be pursued, while data on the first 17 patients will be analyzed.

In order to account for not evaluable patients (+/- 20%), **45 patients will be recruited.**

The anticipated accrual rate is 2-3 patients/months.

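### Section 11.1.8 cites 51 patients where Section 13.2 and the synopsis give 45, and the final rule, correct at 37 evaluable patients, covers no other number

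*Combined protocol and SAP*

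**What the plan says.** Section 13.2 sets an optimal Simon two-stage design for a 20% versus 40% non-progression rate, with 10% type I error and 90% power. The study stops if 3 or fewer of the first 17 assessable patients are progression-free. If not: "Otherwise, the second group of 20 subjects will be recruited". The drug merits further testing if "11 patients or more are progression-free (out of the 37 evaluable patients"). With an allowance of plus or minus 20% for non-evaluable patients, "45 patients will be recruited", and "inclusion will not be suspended after the recruitment of the first 17 patients".

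The synopsis (Number of patients) agrees: "a total of 37 assessable patients will be necessary (17 for the first stage + 20 for the second stage"), with 45 recruited.

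Section 11.1.8 refers to Section 13 and puts the efficacy evaluation after 17 patients "and then once all 51 patients have been included". The two review steps listed just below are tied to six-month information on the first 17 patients and to the end of the study.

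On evaluability, Section 13.2 requires eligibility, a minimum of treatment, and "at least one disease measurement recorded not less than eight weeks after treatment onset". The synopsis (Efficacy evaluations) has the same measurement requirement but exempts early progression. Section 13.1 counts death or progression by six months as failure. Sections 11.1.1 and 13.5.2 each define a main response-rate analysis without the eight-week measurement.

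**The concern.** There are three linked gaps.

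- **The total.** Operative text attributes to the design a number that the design does not contain.
- **The final rule.** It is given for 37 evaluable patients only. Recruitment runs to 45 without a pause, so the evaluable number will vary. Section 13.2 specifies the first 17 for stage 1 but never the first 37 for the final test, and it gives no cut-off for 36 or fewer.
- **The denominator.** Under Section 13.2 as worded, a patient who progresses before eight weeks and has no later measurement is not evaluable. Such patients are failures, so leaving them out raises the observed success rate.

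The stated error rates hold at 37. At other totals they depend on a choice the plan leaves open, and a choice made after outcomes are seen would leave them uncontrolled.

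**Working it through.** **Inputs (Section 13.2).** p0 = 0.20; p1 = 0.40; stage 1 continues with at least 4 of 17; final cut-off c = 11 at n = 37; 45 recruited.

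**Formula.** With n evaluable and cut-off c,

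P(go) = sum over x = 4 to 17 of Bin(x; 17, p) × P[Bin(n − 17, p) ≥ c − x].

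Type I error takes p = 0.20 and power takes p = 0.40.

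**Step 1, the plan's own figure.** At n = 37 and c = 11, type I error is 0.095 and power 0.903. A full search returns this as the optimal design, so the stated test reproduces.

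**Step 2, the totals.**
- 37 × 1.20 = 44.4, rounded up to 45, which is the plan's figure.
- 37 / 0.80 = 46.25, rounded up to 47.
- 51 × 0.80 = 40.8 evaluable; 37 of 51 would mean 1 − 37/51 = 27.5% loss.

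No stated input gives 51.

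**Step 3, cut-off 11 kept at other totals.**

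| Evaluable n | Type I error | Power |
|---|---|---|
| 34 | 0.059 | 0.847 |
| 36 | 0.082 | 0.888 |
| 37 | 0.095 | 0.903 |
| 38 | 0.108 | 0.915 |
| 41 | 0.153 | 0.937 |

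**Step 4, how often n differs from 37.** Assume n is Binomial(45, 1 − loss), with evaluability independent of outcome. Two readings of the allowance are possible: 20% of those enrolled (45 × 0.80 = 36 expected), or the loss built into 45 = 37 × 1.2 rounded up, which is 8/45 = 17.8% (37 expected). Lower losses are shown as a range. The last two columns apply the cut-off of 11 to all evaluable patients.

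| Loss | P(n < 37) | P(n = 37) | P(n > 37) | Average type I error | Average power |
|---|---|---|---|---|---|
| 20% | 0.56 | 0.14 | 0.30 | 0.085 | 0.875 |
| 17.8% | 0.41 | 0.15 | 0.44 | 0.097 | 0.893 |
| 15% | 0.23 | 0.14 | 0.64 | 0.114 | 0.910 |
| 10% | 0.03 | 0.04 | 0.92 | 0.146 | 0.931 |

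**Step 5, cut-offs that hold type I error at or below 10%**, with stage 1 unchanged.

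| Evaluable n | Cut-off | Type I error | Power |
|---|---|---|---|
| 29–33 | ≥10 | 0.048–0.099 | 0.779–0.888 |
| 34–37 | ≥11 | 0.059–0.095 | 0.847–0.903 |
| 38–41 | ≥12 | 0.058–0.091 | 0.871–0.915 |
| 42–45 | ≥13 | 0.057–0.087 | 0.890–0.923 |

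The ranges are tight: a cut-off of 9 at n = 29 gives 0.103, and 10 at n = 34 gives 0.114. Fewer than 29 evaluable has probability 0.004 at 20% loss.

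**Step 6, the denominator.** If a fraction e of patients progress before eight weeks and are dropped, a true rate of 0.20 becomes 0.20 / (1 − e) among those kept. The documents give no value for e. Assuming 10%, the rate is 0.222; assuming 20%, it is 0.25.

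**The case against.** The strongest reply is that the test is already specified. Section 13.2 names 37 evaluable patients as the denominator, and its design figures are right. That stands: the natural reading is a test on 37, and the inflated type I errors in the working require a departure from it. What the reply leaves open is which 37 count when more are evaluable, and what cut-off applies below 37.

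Four stronger readings are tempting, and the documents do not support them.

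- *The trial will be run and tested on 51.* At 20% loss that would give an average type I error of 0.151, but neither sample-size passage plans 51 and the review triggers in Section 11.1.8 do not use it.
- *A shortfall is the likelier case.* This holds at 20% loss. At the 17.8% implied by the plan's own arithmetic, the chances are 0.41 below 37 and 0.44 above.
- *Type I error exceeds 10% under the plan.* Averaged over the planned loss, it does not, even with the cut-off of 11 applied to everyone.
- *Section 13.5.2 sets up a rival decision set.* Section 11.1.1 uses the same term for the main response-rate analysis under the heading of objective response, so Section 13.5.2 may concern best overall response and not the six-month decision. A clarifying sentence is warranted; a finding of contradiction is not.

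The difference between Section 13.2 and the synopsis on early progression has no such explanation.

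**Conclusion.** The point holds in a limited form. The figure 51 is an inconsistent sample size in operative text. The final rule is correct at 37 but incomplete, since exactly 37 has probability of about 0.15 at the planned loss.

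The effect on error rates is small if loss runs to plan: average type I error 0.085 to 0.097 and power 0.875 to 0.893. Type I error is materially inflated only if loss is well below plan and the cut-off of 11 is applied to all evaluable patients.

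The early-progression conflict is real, and it acts in one direction by taking failures out of the denominator. Its size cannot be derived from the documents.

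The averages assume independent loss and evaluability unrelated to outcome. The eight-week requirement makes the second assumption doubtful. The point should be fixed, but the design itself stands.

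**What to change.** 1. Reconcile the 51 in Section 11.1.8 with Section 13.2 and the synopsis. Both support 45; the sponsor should confirm.
2. Add to Section 13.2: *The decision uses the first 37 evaluable patients in order of inclusion; later evaluable patients contribute to estimation only. If fewer than 37 are evaluable, the stage 1 rule is unchanged and the final cut-off is the smallest that keeps exact type I error at or below 10% (at least 11 for 34 to 37, at least 10 for 29 to 33). Attained type I error and power are reported.* A valid alternative above 37 is to test all evaluable patients, with at least 12 for 38 to 41 and at least 13 for 42 to 45.
3. Carry the synopsis's early-progression exemption into the Section 13.2 definition of evaluable, so that early progressions count as failures. State in Section 13.5.2 that the decision set is the one in Section 13.2.

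**Cost.** An amendment, needing ethics committee and authority approval if it counts as a change to principal methods (Section 15.1). No extra patients are needed, but some evaluable patients may not enter the decision. At 20% loss the first-37 rule averages type I error 0.084 and power 0.884, against 0.085 and 0.875 for a cut-off of 11 on everyone. At 10% loss it gives 0.094 and 0.902, against 0.146 and 0.931.

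**Timing.** Planned inclusion ended in September 2012 (Section 1.3) and Section 7.1 carries a December 2016 safety list. The sponsor should state whether outcome data have already been examined. If so, any shortfall cut-off should be labelled post hoc.

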12. DATA REPORTING / REGULATORY REQUIREMENTS

Adverse event lists, guidelines, and instructions for AE reporting can be found in [Section 7.0](#) (Adverse Events: List and Reporting Requirements).

12.1. Data Reporting

12.1.1 Method

This study will be monitored by the Clinical Data Update System (CDUS) version 4.2. Cumulative CDUS data will be submitted quarterly to CTEP by electronic means. Reports are due January 31, April 30, July 31, and October 31. Instructions for submitting data using the CDUS can be found on the CTEP web site (<http://ctep.cancer.gov>). **Note:** All adverse events that have occurred on the study, including those reported through CTEP-AERS, must be reported via CDUS.

12.1.2 Responsibility for Data Submission

Study participants are responsible for submitting CDUS data and/or data forms to the Coordinating Center quarterly by *January 31, April 30, July 31, and October 31* to allow time for Coordinating Center compilation, Principal Investigator review, and timely submission to CTEP (see [Section 12.1.1](#)).

The Coordinating Center is responsible for compiling and submitting CDUS data to CTEP for all participants and for providing the data to the Principal Investigator for review.

12.2. CTEP Multicenter Guidelines

This protocol will adhere to the policies and requirements of the CTEP Multicenter Guidelines. The specific responsibilities of the Principal Investigator and the Coordinating Center (Study Coordinator) and the procedures for auditing are presented in [Appendix B](#).

- The Principal Investigator/Coordinating Center is responsible for distributing all IND Action Letters or Safety Reports received from CTEP to all participating institutions for submission to their individual IRBs for action as required.
- Except in very unusual circumstances, each participating institution will order DCTD-supplied agents directly from CTEP. Agents may be ordered by a participating site only after the initial IRB approval for the site has been forwarded by the Coordinating Center to the CTEP PIO ([contact]) (except for Group studies).

12.3. Cooperative Research and Development Agreement (CRADA)/Clinical Trials Agreement (CTA)

The agent(s) supplied by CTEP, DCTD, NCI used in this protocol is/are provided to the NCI under a Collaborative Agreement (CRADA, CTA, CSA) between Genentech and the NCI Division of Cancer Treatment and Diagnosis. Therefore, the following obligations/guidelines, in addition to the provisions in the Intellectual Property Option to Genentech@ (<http://ctep.cancer.gov/industry>) contained within the terms of award, apply to the use of the Agent(s) in this study:

1. Agent(s) may not be used for any purpose outside the scope of this protocol, nor can Agent(s) be transferred or licensed to any party not participating in the clinical study. Genentech data for Agent(s) are confidential and proprietary to Genentech and shall be maintained as such by the investigators. The protocol documents for studies utilizing investigational Agents contain confidential information and should not be shared or distributed without the permission of the NCI. If a copy of this protocol is requested by a patient or patient's family member participating on the study, the individual should sign a confidentiality agreement. A suitable model agreement can be downloaded from: <http://ctep.cancer.gov>.
2. For a clinical protocol where there is an investigational Agent used in combination with (an)other investigational Agent(s), each the subject of different collaborative agreements, the access to and use of data by each Genentech shall be as follows (data pertaining to such combination use shall hereinafter be referred to as "Multi-Party Data.@):
 - a. NCI will provide Genentech with prior written notice regarding the existence and nature of any agreements governing their collaboration with NIH, the design of the proposed combination protocol, and the existence of any obligations that would tend to restrict NCI's participation in the proposed combination protocol.
 - b. Genentech shall agree to permit use of the Multi-Party Data from the clinical trial by any

other collaborator solely to the extent necessary to allow said other Genentech to develop, obtain regulatory approval or commercialize its own investigational Agent.

- c. Genentech having the right to use the Multi-Party Data from these trials must agree in writing prior to the commencement of the trials that it will use the Multi-Party Data solely for development, regulatory approval, and commercialization of its own investigational Agent.

Clinical Trial Data and Results and Raw Data developed under a Collaborative Agreement will be made available exclusively to Genentech, the NCI, and the FDA, as appropriate and unless additional disclosure is required by law or court order. Additionally, all Clinical Data and Results and Raw Data will be collected, used, and disclosed consistent with all applicable federal statutes and regulations for the protection of human subjects including, if applicable, the Standards for Privacy of Individually Identifiable Health Information set forth in 45 C.F.R. Part 164.

4. When Genentech wishes to initiate a data request, the request should first be sent to the NCI, who will then notify the appropriate investigators (Group Chair for Cooperative Group studies, or PI for other studies) of Genentech's wish to contact them.
5. Any data provided to Genentech for Phase 3 studies must be in accordance with the guidelines and policies of the responsible Data Monitoring Committee (DMC), if there is a DMC for this clinical trial.
6. Any manuscripts reporting the results of this clinical trial must be provided to CTEP by the Group office for Cooperative Group studies or by the principal investigator for non-Cooperative Group studies for immediate delivery to Genentech for advisory review and comment prior to submission for publication. Genentech will have 30 days from the date of receipt for review. Genentech shall have the right to request that publication be delayed for up to an additional 30 days in order to ensure that Genentech's confidential and proprietary data, in addition to Genentech's intellectual property rights, are protected. Copies of abstracts must be provided to CTEP for forwarding to Genentech for courtesy review as soon as possible and preferably at least three (3) days prior to submission, but in any case, prior to presentation at the meeting or publication in the proceedings. Press releases and other media presentations must also be forwarded to CTEP prior to release. Copies of any manuscript, abstract and/or press release/ media presentation should be sent to:

Regulatory Affairs Branch, CTEP, DCTD, NCI
[name]
[name]
[contact]
Email: [contact]

The Regulatory Affairs Branch will then distribute them to Genentech. No publication, manuscript or other form of public disclosure shall contain any of Genentech's confidential/

proprietary information.

13. STATISTICAL CONSIDERATIONS

13.1 Study Design/Endpoint

We will rely on a two-stage Simon's design with the 6-month clinical benefit (CR + PR + SD) rate as the primary endpoint. At six months, patients will be classified as success (Alive at 6 months AND CR/PR/ SD) or failure (dead OR alive with progression).

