| SAFETY EVALUATIONS | 
Patients will be evaluable for safety if they have received at least one dose of GDC-0449. All AEs will be graded according to the CTEP CTCAE Version 4.0. Safety profile will be continuously followed during treatment and up to 30 days after the last GDC-0449 dose or until the start of a new antitumor therapy, whichever occurs first.
 |
| TRANSLATIONAL RESEARCH PROGRAM | 
The following analyses will be done on tumor samples from patients treated with GDC-0449:
 
 - Analysis of the mutational status of PTCH and SMO - Analysis of the expression pattern of hedgehog signaling molecules (Shh, PTCH, SMO, GLI-1, GLI-2, GLI-3) by using quantitative reverse transcription-polymerase chain reaction and immunohistochemistry (IHC). 
The 6-months clinical benefit rate will be correlated with the mutational status of PTCH and SMO and with the expression score of hedgehog signaling molecules in order to identify predictive factors of clinical benefit from GDC-0449.
 |

TABLE OF CONTENTS

| | |
|---|----|
| SUMMARY OF CHANGES | I |
| SYNOPSIS | 3 |
| TABLE OF CONTENTS | 7 |
| 1. OBJECTIVES | 11 |
| 1.1. Primary Objective | 11 |
| 1.2. Secondary Objectives..... | 11 |
| 1.3. Study design and calendar..... | 11 |
| 2. BACKGROUND | 11 |
| 2.1 Study Disease..... | 11 |
| 2.2 GDC-0449..... | 12 |
| 2.3 Rationale | 21 |
| 2.4 Correlative Studies Background | 21 |
| 3. PATIENT SELECTION | 22 |
| 3.1 Eligibility Criteria | 22 |
| 3.2 Exclusion Criteria | 23 |
| 3.3 Inclusion of Women and Minorities | 24 |
| 4. REGISTRATION PROCEDURES..... | 24 |
| 4.1. General Guidelines..... | 24 |
| 4.2. Registration Process..... | 25 |
| 5. TREATMENT PLAN..... | 26 |
| 5.1 Agent Administration | 26 |
| 5.1.1 GDC-0449..... | 26 |
| 5.2 General Concomitant Medication and Supportive Care Guidelines..... | 26 |
| 5.2.1 GDC-0449..... | 26 |
| 5.3 Duration of Therapy..... | 28 |
| 5.4 Duration of Follow Up..... | 28 |
| 5.5 Criteria for removal from Study..... | 28 |
| 6. DOSING DELAYS/DOSE MODIFICATIONS | 28 |
| 7. ADVERSE EVENTS: LIST AND REPORTING REQUIREMENTS..... | 29 |
| 7.1 Comprehensive Adverse Events and Potential Risks Lists (CAEPRs) for GDC-0449 | 29 |
| 7.2 Adverse Event Characteristics [Following NCI procedures] | 33 |
| 7.3. Expedited Adverse Event Reporting [Following NCI procedures] | 33 |

| | | |
|--------------|---|----|

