5. TREATMENT PLAN

5.1 Agent Administration

Treatment will be administered on an outpatient basis. Reported adverse events and potential risks for GDC-0449 are described in [Section 7](#). Appropriate dose modifications for GDC-0449 are described in [Section 6](#). No investigational or commercial agents or therapies other than those described below may be administered with the intent to treat the patient's malignancy.

| REGIMEN DESCRIPTION | | | | | |
|----------------------------|--|-------------|--------------|-----------------|---------------------|
| Agent | Premedications; Precautions | Dose | Route | Schedule | Cycle Length |
| GDC-0449 | Take with or without food at the same time every day | 150 mg | PO | Days 1-28 | 4 weeks (28 days) |

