7.8. Non serious adverse events [Following Institut Bergonié procedures]

| TYPE OF EVENT | REPORTING PROCEDURES | DEADLINE FOR REPORTING TO THE SPONSOR |
|----------------|-------------------------|--|
| Non-serious AE | Case report/record form | Does not need to be reported immediately |

Non-serious adverse events will be reported by the investigator in the patient’s CRF and will be followed-up until complete resolution. The CTEP Version 4.0 of the NCI Common Terminology Criteria for Adverse Events (CTCAE) will be utilized for AE reporting. The CTEP Version 4.0 of the CTCAE is identified and located on the CTEP website at (http://ctep.cancer.gov/protocolDevelopment/electronic_applications/ctc.htm). All appropriate treatment areas should have access to a copy of the CTEP Version 4.0 of CTCAE.

If an adverse event becomes serious, it should be reported and followed-up as mentioned in the previous reporting procedures.

If the investigator would like to decrease trial treatment dose or temporarily stop study management without respecting protocol procedures, he/she should have previously discussed with the coordinator.

However, symptomatic treatment can be prescribed to manage the adverse event.

Any definitive interruption of the procedure has to be immediately notified to the sponsor. The patient remains in the study and is followed-up according to the procedures described in the protocol.

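### The 6-month success rule takes no account of other antitumour treatment started before the assessment, so one patient stable on a later therapy can be credited to GDC-0449 and tip either Simon boundary

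*Combined protocol and SAP*

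**What the plan says.** - **Primary endpoint (13.1).** "At six months, patients will be classified as success (Alive at 6 months AND CR/PR/ SD) or failure (dead OR alive with progression"). The rule refers to vital status and disease status only, not to the treatment the patient is then receiving.
- **Decision rule (13.2).** The hypotheses are "20% non-progression rate (null hypothesis") and "40% acceptable non-progression rate (alternative hypothesis"), with "10% type I error rate" and 90% power. The trial stops at 3 or fewer successes in 17 and declares the drug worth pursuing at 11 or more in 37.
- **Evaluability (13.2).** An eligible patient needs one complete or two incomplete cycles and one disease measurement at 8 weeks or later.
- **Stopping drug (5.3).** Several of the listed reasons do not involve progression: adverse events, intercurrent illness, the patient's decision, the investigator's judgement.
- **After stopping.** Section 7.8 says of a definitive interruption: "The patient remains in the study and is followed-up according to the procedures described in the protocol". Section 5.5 says that patients meeting any 5.3 criterion are removed from study. The synopsis schedules imaging every 8 weeks until progression, without reference to end of drug.
- **Other antitumour therapy.** Section 5.1 says: "No investigational or commercial agents or therapies other than those described below may be administered with the intent to treat" the malignancy. It gives no scoring consequence and does not address the period after GDC-0449 ends. The synopsis closes the safety window 30 days after the last dose "or until the start of a new antitumor therapy, whichever occurs first". No efficacy section uses that event.
- **PFS (11.1.6).** "PFS is defined as the duration of time from start of treatment to time of progression or death, whichever occurs first". Section 13.4 adds Kaplan-Meier estimation and no censoring rule.

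**The concern.** The trial is single-arm and its conclusion rests on a count. The count supports a statement about GDC-0449 only if a success can reasonably be attributed to GDC-0449. Under 13.1 as written, a patient who took one cycle, stopped for toxicity, moved to another agent and was stable at month 6 scores the same as a patient who took GDC-0449 throughout. There is no control arm in which the same thing would happen and cancel out.

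The plan foresees new antitumour therapy, since the safety window depends on it. The central review in 11.1.8 does not close the gap: it compares the 6-month scan with baseline, and neither the referral form nor the response form (Appendices JB and JC) has a field for treatment given on study. At stake are the stage 1 decision, the final go decision and the reading of the 1- and 2-year PFS estimates.

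**Working it through.** **Inputs from 13.2.** Null rate 0.20, alternative 0.40, n1 = 17, n = 37, continue if at least 4/17, go if at least 11/37.

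**Formula.** With X1 ~ Bin(17, p) and X2 ~ Bin(20, p) independent,

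P(go | p) = Σ over x = 4,…,17 of P(X1 = x) × P(X2 ≥ 11 − x).

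**Step 1: reproduce the plan.** P(go | 0.20) = 0.095 and P(go | 0.40) = 0.903. The probability of stopping at stage 1 under the null is 0.549. A full search for the optimal two-stage design under the stated limits returns the same design (3/17, 10/37). The plan's own figures are correct.

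**Step 2: is the route open?** The sections line up as follows.

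| Step | Section | Open? |
|---|---|---|
| Stop without progression | 5.3 | yes |
| Still among the 37 | 13.2 | yes, after one cycle and one scan at 8 weeks or later |
| Still scanned at month 6 | Synopsis and 7.8 | yes |
| Still scanned at month 6 | 5.5 | doubtful: removed from study |
| New therapy changes the classification | 13.1, 11.1.4, 11.1.8, 13.4 | no rule |

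**Step 3: one credited patient.** Suppose one patient is scored a success through other therapy and all others have the null rate of 0.20.

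- In stage 2: X1 ~ Bin(17, 0.2) must be at least 4, and X1 + 1 + Bin(19, 0.2) must be at least 11. P(go) = 0.146.
- In stage 1: 1 + Bin(16, 0.2) must be at least 4, and the total with Bin(20, 0.2) must be at least 11. P(go) = 0.160.
- One in each stage: P(go) = 0.238.

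In counts, one patient turns 3/17 (stop) into 4/17 (continue), or 10/37 (no go) into 11/37 (go). One patient is 1/37 = 2.7 percentage points.

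**Step 4: the same as a rate.** The documents give no frequency, so the net addition to the scored rate is an assumed range.

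| Assumed net addition to a true 20% | Scored rate | P(go) |
|---|---|---|
| 0 points | 20% | 0.095 |
| 1 point | 21% | 0.124 |
| 2 points | 22% | 0.158 |
| 5 points | 25% | 0.285 |
| 10 points | 30% | 0.540 |

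A net addition of 1 point is already enough to pass 10%. The 10-point row would need about 0.10 × 37 = 3.7, so about 4 patients, whose success was due to other therapy.

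**The case against.** **Status after stopping.** The strongest reply is that 5.5 removes from study the very patients in question, and 5.4 then provides 3-monthly follow-up with no imaging mentioned. On that reading there may be no 6-month scan. Section 13.1 does not place a living patient without an assessment in either class, and 13.5.2 has an unknown category. This stands in part: credit to GDC-0449 is the literal result for patients who are scanned, not a certain result for everyone who stops. It does not remove the problem, because 7.8 and the synopsis point the other way.

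**Frequency.** Section 2.1 says that conventional cytotoxics and radiotherapy are generally not effective in this setting, and 13.2 notes the lack of a standard treatment. This favours the low end of the range.

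**Choice of estimand.** Counting outcomes whatever treatment follows is a legitimate choice if stated in advance. It is not stated here, and in a single-arm trial it weakens attribution.

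**Stronger readings that the documents do not support.**
- A reader might infer that later therapy can carry PFS over the go threshold. PFS has no threshold; it is a descriptive secondary endpoint.
- A reader might infer that every patient who switches is a failure turned into a success. A patient who would have been stable anyway is not misclassified.
- A reader might infer that resecting or irradiating a target lesion reliably reads as stable disease or response. Section 5.1 may bar it while on drug, and Table 1 in 11.1.4 gives NE when target lesions are not all evaluated and non-target disease has not progressed.
- A reader might infer that the start date of new therapy is not collected. The CRF is not among the documents, the calendar is offered only as an example, and the safety window already needs that date.

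**Conclusion.** The point holds in limited form. The primary rule in 13.1 and the PFS definition in 11.1.6 say nothing about antitumour therapy started before progression. Applied literally, 13.1 can credit that therapy to GDC-0449. One such patient is enough to cross either boundary and takes the false-go probability from 0.095 to 0.146 or 0.160, above the stated 10%.

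Those two figures assume exactly one patient scored a success through other therapy, with everyone else at 20%. The documents give no basis for saying how many such patients to expect, and the number may be zero. The 1- and 2-year PFS estimates may be biased upward for the same reason, by an amount that cannot be computed from the documents. The conflict between 5.5 and 7.8 is a separate defect that decides whether these patients have a 6-month assessment at all. The change should be made before analysis, but the design itself is sound.

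**What to change.** 1. **13.1.** Add that a patient who starts any other antitumour treatment (systemic therapy, radiotherapy, or surgery or ablation of a tumour lesion) before the 6-month assessment is classified as a failure in the primary count. Add a sensitivity analysis that counts outcomes regardless of later therapy.
2. **11.1.6 and 13.4.** State one rule for new antitumour therapy in PFS, either an event or censoring at the last adequate assessment before it, and report the other as a sensitivity analysis. If the PFS rule differs from the primary rule, say why.
3. **Data.** Record the type and start date of any new antitumour therapy at the existing off-treatment visit and the 3-monthly contacts in 5.4.
4. **Consistency.** Reconcile 5.5 with 7.8 on the status of a patient who stops drug without progression, and say whether 6-month imaging is still obtained.

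**Cost.** A few sentences and one CRF item. The sample size (17, then 37) and the boundaries (at least 4, then at least 11) do not change. The statistical cost is power, if some patients who switch were true GDC-0449 successes. With a true rate of 40%, power falls from 0.903 to 0.858 if the scored rate is 38%, and to 0.764 if it is 35%. The sensitivity analysis in item 1 shows how far the result depends on that choice.
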